6. ASSESSMENT OF SAFETY

Due to the pre-emptive treatment of a patient population normally not treated, an independent DSMB assessment of infectious risk and adverse events on an ongoing basis during enrollment is included. The trial may be stopped based on the decision by the independent DSMB if increased infectious risk or AE risk is considered to outweigh the potential benefit. For these safety assessments, the treatment period (first 6 cycles of 28 days each) and the follow up period will be assessed independently to improve detection of treatment-related events vs CLL-related events. The following early stopping rules will be applied:

- Any fatal events or Grade ≥3 infectious events in the treatment arm will be reported immediately (within 7 days of notification) to the DSMB for assessment of whether the event impacts the risk-benefit of the treatment (data on similar events in the observation arm will be made available to the DSMB). All Grade ≥3 infectious events would be considered AESIs to be reported along with SAEs within 24 h in the phase 2 part.
- Assuming the incidence of grade ≥3 infectious events is the same in the treatment arm and
 the observation arm, which based on the predictive model is 10% within the first 6 months, a
 non-inferiority test can be performed. With a power of 80% and a sample size of 25 patients
 in each arm, the margin for assessment of non-inferiority will be 21%, i.e. if significantly more

infections are seen in the treatment arm than in the observation arm, the treatment arm will be inferior to observation.

- Any pattern of AEs or individual AEs through the above-mentioned DSMB assessment that indicate that the trial should be stopped.
- A thorough translational immune phenotype and immune function analysis plan is adjoined to the study. Results of this translational program are included as secondary outcomes. The assessment of the grade ≥3-infection free, CLL-treatment-free survival will be qualified by the results from the translational program. Hereby, the clinical outcome from the study will be significantly strengthened by molecular and functional information about improvements in immune function.

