Randomization has to occur within 42 days after the first tests for screening were performed. Patients will be randomly assigned to treatment vs observation through 1:1 randomization process with stratification according to country, TP53 aberration status and IGHV mutational status. Treatment or observation period has to be initiated within 14 days after randomization.

Acalabrutinib 100 mg BID from cycle 1 day 1 for 3 cycles of 28 days. Due to the preemptive treatment within the trial of patients not fulfilling IWCLL criteria for treatment of CLL, the tumor burden will be lower than in other trial populations, thus it is assessed safe to start acalabrutinib and venetoclax treatment simultaneously.

Venetoclax, ramp up during the first five weeks starting cycle 1 day 1, 7 days treatment on each dose level (20-50-100-200-400 mg), thereafter 400 mg once daily for a total of 3 cycles of 28 days counted from cycle 1 day 1.

The trial is a phase 2 trial with a non-inferiority analysis for safety.

Efficacy and Safety Parameters:

Due to the pre-emptive treatment of a patient population normally not treated, an independent Data Safety Monitoring Board (DSMB) will assure ongoing assessment of infectious risk and adverse events. The trial may be stopped based on the decision by the independent DSMB if increased infectious risk or AE risk is considered to outweigh the potential benefit during enrollment. For these safety assessments, the treatment period (first 3 cycles of 28 days each) and the follow up period will be assessed independently to improve detection of treatment-related events vs late treatment-related events and CLL-related events. The following early stopping rules will be applied:

- Any fatal events or Grade ≥3 infectious events in the treatment arm will be reported immediately (within 7 days of notification) to the DSMB for assessment of whether the event impacts the risk-benefit of the treatment (data on similar events in the observation arm will be made available to the DSMB). All Grade ≥3 infectious events would be considered AESIs to be reported along with SAEs within 24 h in the phase 2 part.

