3.2 STUDY TREATMENT

3.2.1 Treatment Schedule (see figure for outline)

Acalabrutinib 100 mg BID from cycle 1 day 1 for 3 cycles of 28 days.

[figure not shown]
Venetoclax, ramp up during the first five weeks starting cycle 1 day 1, 7 days treatment on each dose level (20-50-100-200-400 mg), thereafter 400 mg once daily until a total of 3 cycles of 28 days counted from cycle 1 day 1.

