3.4.2 Safety Parameters

Due to the pre-emptive treatment of a patient population normally not treated, an independent Data Safety Monitoring Board (DSMB) will assure ongoing assessment of infectious risk and adverse events. The trial may be stopped based on the decision by the independent DSMB if increased infectious risk or AE risk is considered to outweigh the potential benefit during enrollment. Extensive assessment of immune function including phenotyping of immune cells, cytokine profiling and functional assays of immune function will be performed along with assessment of MRD and subclonal development. Infections will be closely monitored for the first 2 years, thus

including the 18-months follow up. Follow up will be aligned for the treatment arm and the observation arm to avoid registration bias.

For consistency of interpretation, AEs and laboratory results will be coded using the Medical Dictionary for Regulatory Activities (MedDRA), and the severity of AEs will be graded using the Common Terminology Criteria for Adverse Events (CTCAE), Version 5. Standard definitions for seriousness will be applied.

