3.8 STUDY TREATMENT SCHEDULE

Acalabrutinib will be administered orally 100 mg twice daily, every day from cycle 1 day 1 for 3 cycles of 28 days each.

Venetoclax, ramp up during the first five weeks starting cycle 1 day 1, 7 days treatment on each dose level (20-50-100-200-400 mg), thereafter 400 mg once daily for a total of 3 cycles of 28 days counted from cycle 1 day 1.

Please see section 3.9 for management of dosing delays and modifications.

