3.9 DURATION OF THERAPY

Duration of treatment with acalabrutinib and venetoclax is for 3 cycles of 28 days; the end of trial is defined as seven years after start of treatment or observation with close follow up for the first two years, while follow up for AESI's, CLL treatment and survival continues until end of trial. The primary endpoint for the phase 2 part is 6 months after start of treatment or observation.

3.10 DOSING DELAYS AND MODIFICATIONSIn the case of AEs attributed to both acalabrutinib and venetoclax, the local investigator should decide whether dose

modifications apply to one or both drugs in collaboration with the sponsor, as no data on pharmacokinetic interaction between acalabrutinib and venetoclax are currently available.

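### The treatment period for the DSMB safety assessments is 6 cycles in Section 6 but 3 cycles in the synopsis and in every dosing section

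*Protocol*

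**What the plan says.** The rule stands twice in the current text. In the synopsis, under Efficacy and Safety Parameters, it reads "the treatment period (first 3 cycles of 28 days each) and the follow up period will be assessed independently". In Section 6 it reads "the treatment period (first 6 cycles of 28 days each) and the follow up period will be assessed independently". The synopsis gives the purpose as better detection of treatment-related events, as against late treatment-related and CLL-related events. Section 6 gives the same purpose without the late treatment-related category.

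The dosing text is uniform:

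- Section 3.9: "Duration of treatment with acalabrutinib and venetoclax is for 3 cycles of 28 days".
- Section 3.2.1, acalabrutinib: "Acalabrutinib 100 mg BID from cycle 1 day 1 for 3 cycles of 28 days".
- Section 3.2.1, venetoclax: "thereafter 400 mg once daily until a total of 3 cycles of 28 days counted from cycle 1 day 1".
- Section 3.8, acalabrutinib: "every day from cycle 1 day 1 for 3 cycles of 28 days each".
- The venetoclax table in Section 3.7.5 ends with cycle 3, and Section 5.1 speaks of 3 months.

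Section 3.4.2 says that infections are closely monitored for the first 2 years, "including the 18-months follow up", without naming the starting point of those 18 months.

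**The concern.** The split exists so that the DSMB can look at events under treatment separately from events that come later. It can do so only if the first window matches the time on drug. A window of 6 cycles runs past the scheduled end of dosing and takes in a stretch with no study drug. Events from that stretch would be counted with on-drug events, and the follow-up period would lose them.

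The text is operative. The patients would not normally be treated at this stage, the DSMB may stop the trial on its assessment of infectious and adverse-event risk, and its opinion is one input to the phase 3 decision in Section 5.4. Someone preparing DSMB summaries from Section 6 and someone working from the synopsis would assign the same events to different periods.

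**Working it through.** **1. Length of the two windows.** Section 6: 6 × 28 = 168 days (24 weeks). Synopsis: 3 × 28 = 84 days (12 weeks). Difference: 168 − 84 = 84 days, or 12 weeks.

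**2. Which length matches the dosing schedule.** Sections 3.2.1, 3.7.5, 3.8 and 3.9 give 3 cycles. Three other places agree:

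- Section 2.1 puts the 24-week endpoint 12 weeks after finishing treatment, so dosing lasts 24 − 12 = 12 weeks.
- Section 4.1.17 puts the CT scan 8 weeks after the last dose and 20 weeks after the first, so dosing lasts 20 − 8 = 12 weeks.
- Appendix 1 has visits in cycles 1 to 3, then end of treatment, then a separate 24-week visit.

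No section schedules cycles 4 to 6. The 6-cycle window is therefore not reproduced from the protocol's own schedule. By that schedule its off-drug share is 84/168 = 50%, and it coincides with the 24-week primary-endpoint window.

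**3. Illustration of the effect on a by-period comparison.** Assume a constant hazard in the observation arm. Let *h* be the rate ratio on days 1–84 and *c* the rate ratio on days 85–168. The rate ratio over 168 days is

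(84*h* + 84*c*)/168 = (*h* + *c*)/2.

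- No carry-over (*c* = 1): *h* = 2 gives 1.5, *h* = 3 gives 2.0, *h* = 4 gives 2.5.
- Complete carry-over (*c* = *h*): the ratio stays at *h*, with no dilution.

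So an on-drug ratio of 2 would show as something between 1.5 and 2.0. The documents give neither *h* nor *c*.

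**4. The same in risks and events.** Take the protocol's 10% incidence within 6 months, treated here as 24 weeks, with 25 patients per arm and no carry-over. Observation-arm risk at 12 weeks is 1 − 0.9^0.5 = 5.1%. Treatment-arm risk is 1 − 0.9^(0.5*h*) at 12 weeks and 1 − 0.9^(0.5*h* + 0.5) at 24 weeks.

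| *h* | Risk at 12 weeks, treatment vs observation | Ratio | Risk at 24 weeks | Ratio |
|---|---|---|---|---|
| 2 | 10.0% vs 5.1% | 1.95 | 14.6% vs 10.0% | 1.46 |
| 3 | 14.6% vs 5.1% | 2.85 | 19.0% vs 10.0% | 1.90 |

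For *h* = 2 the expected numbers of patients with an event per 25 are 2.5 vs 1.28 at 12 weeks and 3.65 vs 2.5 at 24 weeks.

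**5. The 18-month phrase.** From the end of 3 cycles to 2 years is about 24 − 3 = 21 months. From a 6-month point to 2 years is 24 − 6 = 18 months. Section 3.9 places the phase 2 primary endpoint at 6 months, so 18 months also fits a count from that endpoint.

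**6. The non-inferiority figures.** With one-sided alpha of 0.05 (an assumption; the protocol states none), the margin is (1.645 + 0.842) × √(2 × 0.1 × 0.9/25) = 0.211, which agrees with the stated 21%. The length of the DSMB treatment period does not enter.

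**The case against.** The strongest reply is that little hangs on the number. Fatal and grade 3 or higher infectious events in the treatment arm go to the DSMB individually within 7 days, with observation-arm data available. Section 6.1.2 records dates and suspected relationship for every adverse event, so the DSMB can see whether an event fell on or off drug, and a wrong split can be redone. No stopping threshold uses a period-specific rate, and the one quantitative rule, the 21% margin, covers the whole 24 weeks. With about 2.5 expected events per arm, ratios of 1.5 and 2.0 could not be told apart. All of this stands. It confines the consequence to the aggregate comparison by period and keeps the severity below must-fix.

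It might also be said that Section 6 means a deliberately wider window. The text does not say so: it names the window the treatment period and counts it in cycles that are not scheduled. Sections 3.4.3.1 and 5.3.5 mention 6 or 3 months as possible optimal treatment lengths, but they set no dosing.

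Three stronger readings are tempting and not supported:

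- A reader might infer that the DSMB's on-drug signal is in fact diluted. That holds only if the Section 6 version is applied, and the protocol does not show which version governs.
- A reader might infer that the 18 months in Section 3.4.2 is an error that fits only a 6-month regimen. It fits a count from the 6-month endpoint equally well.
- A reader might infer that DSMB tables need correcting. None are in the document.

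**Conclusion.** The point holds as an internal inconsistency, rated should-fix. One safety-assessment rule is stated with two lengths, 84 and 168 days, and only the 84-day version agrees with the protocol's dosing sections. As written, the Section 6 window is half off-drug by the protocol's own schedule and works against the purpose given for the split. If it is applied, all events on days 85 to 168 change category.

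The 50% share assumes that dosing runs to schedule; pauses that extend treatment would reduce it. The drop in rate ratio from 2 to 1.5 is an illustration that assumes a constant baseline hazard and no carry-over, and it is an upper bound on dilution when any excess persists after the last dose. Dosing, sample size, the 24-week non-inferiority test and individual event reporting to the DSMB are untouched. The point concerns an analysis window and takes no position on how long treatment should last.

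**What to change.** Reconcile Section 6 with the synopsis and with the dosing text in Sections 3.2.1, 3.7.5, 3.8 and 3.9. Define the DSMB on-treatment window once, make it equal to the scheduled dosing period, and have the other place refer to it. Use the same statement of purpose in both, since only the synopsis names late treatment-related events. If a separate 24-week safety window is also wanted, give it its own name.

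In Section 3.4.2, state the time point from which the 18-month follow-up is counted.

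The cost is one number in Section 6 and one clarifying phrase in Section 3.4.2. No design figure or analysis of the primary endpoint changes.

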6.1 DOCUMENTING AND REPORTING OF ADVERSE AND SERIOUS ADVERSE EVENTS

The investigator is responsible for ensuring that all AEs and SAEs that are observed or reported during the study, as outlined in the prior sections, are recorded on the CRF. The eCRF system assures that the sponsor is notified in real time about SAEs and other AEs that need further reporting to health authorities and the companies providing the investigational drugs. This reporting will follow EU regulations and agreements set out in the contract with the companies.

6.1.1 Adverse Event Reporting Period

The AE reporting period for this study begins when the subject receives the first dose of study drug or Cycle 1 Day 1 for the observation arm of the study and ends with the SFU visit.

6.1.2 Assessment of Adverse Events

Investigators will assess the occurrence of AEs and SAEs at all subject evaluation timepoints during the study. All AEs and SAEs whether volunteered by the subject, discovered by study personnel during questioning, or detected through physical examination, or other means, will be recorded in the subject's medical record and on the AE CRF.

Each recorded AE or SAE will be described by its diagnostic term, duration (e.g., start and end dates), severity, regulatory seriousness criteria, if applicable, suspected relationship to the study drug, and any actions taken.

6.1.3 Pregnancy

The Sponsor should report all pregnancies and pregnancies in the partners of subjects to the Regulatory Authorities per institutional and/or regulatory guidelines, and to the companies providing investigational drugs as per contractual guidelines.

Any uncomplicated pregnancy that occurs with the subject or with the partner of a treated subject during this study will be reported. All pregnancies and partner pregnancies that are identified during or after this study, wherein the estimated date of conception is determined to have occurred from the time of consent to 30 days after the last dose of study medication will be reported, followed to conclusion, and the outcome reported.

Subjects should be instructed to immediately notify the investigator of any pregnancies. Any female subjects receiving study drug who become pregnant must immediately discontinue study drug. The investigator should counsel the subject, discussing any risks of continuing the pregnancy and any possible effects on the fetus.

6.1.4 Expedited Reporting Requirements for Serious Adverse Events

The Sponsor should report all SAEs to Regulatory Authorities per EU regulatory guidelines, and to the companies providing investigational drugs per contractual guidelines.

6.1.5 Reporting Adverse Events of Special Interest

Atrial fibrillation, ventricular arrhythmias, tumor lysis events, infections, disease progression, treatment for CLL, malignancies and bleeding events are adverse events of special interest in this trial.

6.1.6 Type and Duration of Follow-up of Subjects after Adverse Events

All AEs and SAEs that are collected during the protocol-specified AE reporting period should be followed to resolution, or until the investigator assesses the subject as stable or remitted to grade 1 or lower, or the subject is lost to follow-up or withdraws consent.

7. STUDY ADMINISTRATION AND INVESTIGATOR OBLIGATIONS

The Sponsor retains the right to terminate the study and remove all study materials from a study site at any time. Specific circumstances that may precipitate such termination are:

- Unsatisfactory subject enrollment with regard to quality or quantity
- Significant or numerous deviations from study protocol requirements, such as failures to perform required evaluations on subjects and maintain adequate study records
- Inaccurate, incomplete and/or late data recording on a recurrent basis
- The incidence and/or severity of AEs in this or other studies indicating a potential health hazard caused by the study treatment

7.1 INSTITUTIONAL REVIEW BOARD AND INDEPENDENT ETHICS COMMITTEE

The investigator will submit this protocol, the informed consent, current Summary of Product Characteristics, and any other relevant supporting information to the appropriate Ethics Committee, Health Authorities and Data Protection Agencies for review and approval before study initiation. Amendments to the protocol must also be approved as appropriate, before the implementation of changes in this study.

This clinical study was designed and will be implemented in accordance with the protocol, the International Conference on Harmonisation (ICH) Harmonised Tripartite Guidelines for Good Clinical Practices, applicable local regulations (including European Directive 2001/20/EC), and the ethical principles laid down in the Declaration of Helsinki.

7.2 INFORMED CONSENT AND PROTECTED SUBJECT HEALTH INFORMATION AUTHORIZATION

The investigator, or designee, must explain to each subject the purpose and nature of the study, the study procedures, the possible adverse effects, and all other elements of consent as defined in national and local regulations governing informed consent form. Each subject must provide a signed and dated informed consent before enrollment into this study. Signed consent forms must remain in each subject's study file and be available for verification by study monitors at any time.

In accordance to individual local and national subject privacy regulations, the investigator or designee **must** explain to each subject that for the evaluation of study results, the subject's protected health information obtained during the study may be shared with regulatory agencies and IRBs/IECs. It is the investigator's or designee's responsibility to obtain written permission to use protected health information from each subject. If a subject withdraws permission to use protected health information, it is the investigator's responsibility to obtain the withdrawal request in writing from the subject **and** to ensure that no further data will be collected from the subject. Any data collected on the subject before withdrawal will be used in the analysis of study results.

7.3 SUBJECT SCREENING LOG

The investigator will keep a record that lists all subjects considered for enrollment (including those who did not undergo screening) in the study. For those subjects subsequently excluded from enrollment, record the reason(s) for exclusion will be kept.

Subjects not assessed as high-risk according to the CLL-TIM algorithm, will not be included for the clinical trial, but still followed outside the trial at 6-monthly intervals through medical record review and/or registries for infectious adverse events, initiation of CLL treatment and survival.

7.4 CASE REPORT FORMS

Authorized study site personnel will complete eCRFs designed for this study according to the completion guidelines that will be provided. The investigator will ensure that the CRFs are accurate, complete, legible, and completed promptly.

7.5 INVESTIGATIONAL STUDY DRUG ACCOUNTABILITY

Investigational drugs must be kept in a limited access cabinet or space. The study drug must not be used outside the context of the protocol.

7.6 RECORD RETENTION

The investigator and other appropriate study staff are responsible for maintaining all documentation relevant to the study. Mandatory documentation includes copies of study protocols and amendments, IRB/IEC approval letters, signed ICFs, drug accountability records, SAE information, subject files (source documentation) that substantiate entries in CRFs, all relevant correspondence and other documents pertaining to the conduct of the study.

The investigator shall retain study records in accordance with institutional and/or national/local regulations, whichever is longer.

Pregnancy test ⁵		Х	X ⁶				X ⁷	X ⁷	X ⁷					
ECOG Performance	X	Χ												
ECG		Х												
(PET)-CT scan		Х								Χ				Χ
Lab tests														
Hematology		Х	Х	Х	Χ	X	Χ	Χ	X	Χ		X	Х	Χ
Blood chemistry		Х	X	Х	Χ	Χ	Χ	Χ	X	Χ		X	X	Х
Additional chemistry		Х								Х		X	X	Х
Virology		Х								Х		Х	Х	Χ

¹ No laboratory testing except for standard of care based on the discretion of the local investigator, this visit is for informed consent to assemble data for assessment by the CLL-TIM algorithm

² Max 42 days from screening to randomization, however FISH and TP53 mutational results are accepted up to six months prior to randomization, max 14 days from randomization to cycle 1 day 1 (C1D1)

³ Only for treatment arm.

⁴ TLŚ chemistry the day before, 6 h after ramp up dose of venetoclax and the day after (24 h) before next dose of venetoclax

⁵ Only applies for women of child bearing potential

⁶ A negative pregnancy test is required for all women of child bearing potential within 7 days before start of study treatment

⁷ Only applies for the women of child bearing potential in the treatment arm

Biobank blood	Х	X ³	X ³	Χ	Х	Х	Χ	Х	Х	Χ
Central lab										
IGHV, FISH, Recur	Χ									Х
Flow-MRD	Χ					Х	Χ	Х	Х	Χ
PK samples					X8					
Bone marrow										
Biopsy and aspirate	Х			Χ	Х	Х	Χ			Χ
Aspirate biobank	Х						Χ			X ⁹
Microbiome samples										
Feces, saliva, skin, buccal swabs	X					Х	Х			

